Only right turns will be examined, as previous research has found no difference between the kinematics of left and right turns. Participants will follow the path for a randomly selected amount of time between 1 and 3 minutes. After this time has elapsed, the investigator will initiate a slip during a randomized turn on the path in early, middle, or late stance. Participants will be given a seated rest period of 5 minutes between each trial.

Aim 2 Specific Methods

Young healthy participants will undergo treadmill gait and stabilization movement analysis sessions that will last approximately 270 minutes. All participants will be fitted with a form-fitting singlet, a safety harness mounted to the rigging of the CAREN system, lab-provided shoes, and a full- body retroreflective marker set. A load cell placed in line with the safety harness will allow for the quantification of forces exerted on the harness at 80 Hz. Data will be collected with the treadmill set at a comfortable walking speed of 1.3 m/s. A repeated measures design will have participants slip at 3 different times in the gait cycle for each of 5 different uphill/downhill slopes and at 3 times to both feet for 2 cross-slopes for a total of 27 slip episodes (3 phases x 5 slopes that foot doesn't matter + 3 phases x 2 feet x 2 slopes that foot matters).

Specifically, slips will be delivered over sloped ground surface of no slope, ± 5.0 and ± 10.0 degrees slopes in the direction of walking, and 5.0 and 10.0 degrees perpendicular to the direction of walking.

Sloped surfaces will be generated with the CAREN system treadmill, which is capable of pitch and roll ± 16 degrees.⁵⁵ Slip onset will be triggered by the experimenter in a randomized order at early, mid, or late stance. Participants will walk on the prescribed slope and a slip will be triggered on after a randomly predetermined amount of time between 1 and 3 minutes at either early, middle, or late stance.

Participants will be given a seated rest period of 5 minutes between each trial. To quantify the effects of the slip perturbation, whole body angular momentum, COM characteristics, arm movements, and slip characteristics will be derived from the kinematic data.

Statistical Analysis Plan

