For each variable, investigators will test for normality and employ the appropriate parametric or non-parametric descriptive statistics. Histograms and plots for each variable will be made and examined. Statistical hypothesis testing will be done using custom software written in R statistical computing language (R Core Team). General linear mixed-effects model will be used to determine the effects of diverse slip conditions on reactive movements and slip severity measures for all aims. This mixed-effects model will be used to include participants and order as random factors while testing for differences between conditions. For example, even though these data will have repeated measures from the same subject, a linear mixed effect model can resolve those non-independencies by including participants as a random factor and accounting for changes from baseline participant variation. Aim 1: independent variables will be a) turn radius (4 levels: no turn, 2m, 1m, 1/2m), b) slip timing (3 levels: early, mid, and late stance). Aim 2: independent variables will be a) slope (7 levels: no slope, ± 5.3 degrees AP, ± 10.6 degrees AP, ± 5.3 degrees ML, ± 10.6 degrees ML).

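### Slip timing is a designed factor at every Aim 2 slope, but the SAP's Aim 2 model lists slope alone, so timing has no planned test and its variance falls into the slope error

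*Combined protocol and SAP*

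**What the plan says.** Aim 2 Specific Methods makes slip timing an experimental factor. It has "participants slip at 3 different times in the gait cycle for each of 5 different uphill/downhill slopes" and adds slips at three times to both feet on two cross-slopes. The count is spelled out as "3 phases x 5 slopes that foot doesn't matter + 3 phases x 2 feet x 2 slopes that foot matters". Timing is set by the experimenter: "Slip onset will be triggered by the experimenter in a randomized order at early, mid, or late stance".

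The Statistical Analysis Plan describes a linear mixed-effects model for all aims, meant to "include participants and order as random factors while testing for differences between conditions". It then lists the independent variables aim by aim. Aim 1 has turn radius as item a) and, as its second item, "b) slip timing (3 levels: early, mid, and late stance". The Aim 2 list reads "Aim 2: independent variables will be a) slope (7 levels: no slope", continues with the remaining slope levels, and ends. There is no item b).

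**The concern.** A factor that the experimenter controls, and that triples the number of slips at each slope, does not appear in the model for that aim. Two things follow.

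- **No planned test.** Aim 2 has no pre-specified test of stance phase, or of whether the slope effect depends on stance phase. Several outcome families are to be derived (angular momentum, centre of mass, arm movements, slip characteristics), so leaving this modelling choice until the data are seen has a real cost. This point needs no assumed effect size.
- **A blunter slope test.** Real differences between stance phases would be counted as residual noise. The estimated standard error of every slope contrast would be too large, and the slope test would become conservative and lose power.

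**Working it through.** **1. Reproduce the plan's count.** 3 phases × 5 slopes + 3 phases × 2 feet × 2 cross-slopes = 15 + 12 = 27, which matches "for 2 cross-slopes for a total of 27 slip episodes". Each phase occurs once on each of the five uphill/downhill slopes and twice on each cross-slope. Timing is therefore fully crossed with slope and balanced within it, with 27 / 3 = 9 slips per phase per participant.

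**2. What the listed model omits.** Timing main effect: 3 − 1 = 2 df. Slope-by-timing: (7 − 1) × 2 = 12 df, or (9 − 1) × 2 = 16 df if the signed slopes in the SAP are counted as nine levels (1 + 2 + 2 + 2 + 2).

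**3. Bias.** Because timing is balanced within slope, it cancels from slope contrasts. In a simulation of the 27-slip layout with 20 participants, slope estimates with and without timing in the model differed by at most about 3 × 10⁻¹⁴.

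**4. Effect on the slope standard error.** The documents give no sample size, SD, alpha or timing effect. Assumed:
- N = 10, 20 or 30 participants, two-sided 5%, residual SD 1;
- timing effects of −d, 0, +d residual SDs, the same at every slope and in every participant, so the early-to-late difference is 2d;
- no order effect;
- one unadjusted 0.5 SD contrast between two uphill/downhill slopes, three slips each per participant.

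Formulas:
- Omitted timing sum of squares = N × 9 × 2d² = 18Nd².
- Residual df with seven slope levels = 27N − N − 6 = 26N − 6.
- Standard-error multiplier m = √(1 + 18Nd² / (26N − 6)).
- True contrast standard error SE₀ = √(2 / (3N)), whatever the value of d.
- Power = Φ(0.5/SE₀ − t × m), and type I error = 2Φ(−t × m), where t is the two-sided 5% critical value.

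Worked case, N = 20 and d = 0.5: m = √(1 + 90/514) = 1.084; SE₀ = √(2/60) = 0.183; 0.5/SE₀ = 2.739; t = 1.965; power = Φ(2.739 − 2.130) = Φ(0.609) = 73%.

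| d | Early-to-late difference (SD) | m (N = 20) | Power, N = 10 | Power, N = 20 | Power, N = 30 | Type I error, N = 20 |
|---|---|---|---|---|---|---|
| 0 | 0 | 1.00 | 49% | 78% | 92% | 5% |
| 0.25 | 0.5 | 1.02 | 47% | 77% | 91% | 4.5% |
| 0.5 | 1 | 1.08 | 42% | 73% | 89% | 3.3% |
| 1 | 2 | 1.30 | 26% | 57% | 79% | 1.0% |
| 1.5 | 3 | 1.60 | 11% | 34% | 58% | 0.2% |

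**5. Check by simulation.** With 6,000 runs per setting at N = 20, power was 78, 78, 73, 56 and 34%, and type I error was 4.9, 4.5, 3.6, 1.1 and 0.1%, in the order of the table. The actual spread of the contrast stayed at 0.182 to 0.185 for every d, while the mean estimated standard error rose from 0.183 to 0.293. With timing in the model, power returned to about 49, 78 and 92% at N = 10, 20 and 30 for every d. A separate simulation at N = 20 gave a slope-only residual variance of 1.17 at d = 0.5 and 1.70 at d = 1, against about 1.00 with timing fitted.

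**6. The test that is not planned.** For an early-to-late difference D with mid stance halfway, the 2-df timing test has noncentrality 18N(D/2)². At D = 0.5 SD this is 11.25 for N = 10 and 22.5 for N = 20, giving power of about 86% and 99%. At D = 0.25 SD, power is about 30% and 55%. The design is therefore well able to detect a moderate timing effect.

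**The case against.** The strongest reply is that the omission is a dropped list item. The plural noun before a lone a), the parallel Aim 1 list, and the general statement that the model examines diverse slip conditions in all aims suggest that timing was meant to be included. That is probably true. But the general wording names no factor, the aim-specific list is what defines the model, and an analyst who follows it would fit slope alone.

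Other points stand as limits:

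- **The harm to slope is lost precision only.** False positives are not inflated. The loss is 1 to 2 percentage points at d = 0.25 and 3 to 7 points at d = 0.5. The large losses need early-to-late differences of 2 to 3 residual SDs, which nothing in the documents supports or excludes.
- **Unbiasedness depends on complete data.** Missing or mistimed slips would break the balance, and the slope estimates could then absorb some of the timing effect.
- **The interaction gap is shared.** Aim 1 names no interaction either. Only the missing timing main effect is peculiar to Aim 2.
- **Listing timing does not by itself make its test confirmatory**, since the text gives no Aim 2 hypothesis, primary outcome or alpha.
- **The power figures are simplified.** They concern one unadjusted pair out of the 21 that seven levels allow, and leave out the random order term and any participant-by-timing variation.

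None of this puts timing into the listed Aim 2 model.

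**Conclusion.** The concern holds. The design crosses three slip timings with every Aim 2 slope, and the listed Aim 2 model contains slope only. Timing and slope-by-timing therefore have no pre-specified test, and any timing effect is treated as error in the slope comparison. The first consequence follows from the text alone and is the main reason to act. The second is conditional: under the assumptions above it ranges from no loss, when timing has no effect, to a fall in power from 78% to 34% at N = 20 when early and late stance differ by 3 residual SDs.

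**What to change.** In the Aim 2 list of the Statistical Analysis Plan, add the item that Aim 1 already has, "b) slip timing (3 levels: early, mid, and late stance", and state that slope, timing and slope-by-timing are fixed effects, with participant and order as random factors as now. It would be consistent to say at the same time whether Aim 1 includes its radius-by-timing interaction.

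The same line should say how the slipped foot is handled, since the design has "3 phases x 2 feet x 2 slopes that foot matters". The SAP states seven slope levels but its signed list gives nine, and 9 × 3 = 27, so the mediolateral signs may stand for foot. If they do not, foot should be listed as a factor on the cross-slopes.

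The cost is one line of SAP text and no new data. Timing plus its interaction uses 2 + 12 = 14 df with seven slope levels, or 2 + 16 = 18 with nine. At an assumed N = 10 that leaves 26 × 10 − 20 = 240 or 26 × 10 − 26 = 234 residual df.

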Title: Mechanisms of Fall Resistance to Diverse Slipping Conditions

NCT03758040

11 Mar 2021

Study Protocol

For all gait collections, participants will arrive at the Biomechanics Research Building on the University of Nebraska at Omaha campus. All participants will be consented and screened prior to gait testing. During the consent process, participants will be asked if they can be contacted again for future research studies. During the screening, participants will undergo a short medical history.

Participants will be asked to put on a form fitting suit for data collection. Body weight, height and extremity anthropometry will be collected (length of arm and leg segments). Retroreflective markers will be placed on the legs, arms, torso and head to obtain whole-body kinematic data. A ceiling-mounted safety harness will also be fitted to each participant. Prior to performing any walking trials, the participants will be allowed to "sit" in the harness to experience how it feels when it catches them.

Aim 1 Specific Methods

Young healthy participants will undergo overground gait and stabilization movement analysis sessions that will last approximately 210 minutes. All participants will be fitted with a form-fitting singlet, ceiling mounted safety harness, lab-provided shoes, and a full-body retroreflective marker set. A load cell placed in line with the safety harness will allow for the quantification of forces exerted on the harness at 80 Hz. A 17 camera 3D motion capture system will be used to collect kinematic data at 120 Hz throughout each trial. Data will be collected at a comfortable walking speed of 1.3 m/s. Walking speed will be monitored using timing gait plates placed along the path. Participants will be coached to maintain prescribed walking speed. A repeated measures design will have participants slip both feet at 3 different times in the gait cycle for each of 3 path curvatures for a total of 18 slip episodes. Slips will be delivered while walking along a straight path (infinite radius), or curved paths with radii of 2 or 1 meters. A path consisting of multiple turns will be marked on the floor of the lab, including turning radii of 2 and 1 meters.

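### The Aim 2 model in the SAP does not match the Aim 2 design: its slope list counts to nine rather than seven, and neither slip timing nor slipped foot is named

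*Combined protocol and SAP*

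**What the plan says.** The Statistical Analysis Plan defines the Aim 2 predictors as "slope (7 levels: no slope, ± 5.3 degrees AP, ± 10.6 degrees AP, ± 5.3 degrees ML, ± 10.6 degrees ML". This is item a), and there is no item b). For Aim 1 the same section does give a second item, "b) slip timing (3 levels: early, mid, and late stance". The model is to "include participants and order as random factors while testing for differences between conditions", so participant and order are the only other terms named.

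Aim 2 Specific Methods gives the surfaces as "no slope, ± 5.0 and ± 10.0 degrees slopes in the direction of walking, and 5.0 and 10.0 degrees perpendicular" to the walking direction. On timing it says "Slip onset will be triggered by the experimenter in a randomized order at early, mid, or late stance". On foot, participants are slipped "at 3 times to both feet for 2 cross-slopes for a total of 27 slip episodes", and the cross-slope part of that total is written as "3 phases x 2 feet x 2 slopes that foot matters". The five surfaces along the walking direction are described as ones where the foot does not matter.

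**The concern.** Three parts of the SAP's Aim 2 specification do not fit the design.

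- **Level count.** The SAP states seven levels, but its list carries ± on both ML entries. The protocol's cross-slopes are unsigned.
- **Slip timing.** It is varied in every Aim 2 slip but is not listed as an Aim 2 factor.
- **Slipped foot.** The protocol singles it out on the cross-slopes and spends extra slips on it, but the SAP has no foot term.

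A model fitted exactly as listed, with seven levels, cannot estimate the timing effect or the foot effect. Both would fall into the residual and inflate the estimated standard errors of the surface comparisons. An analyst could also defend several models (seven slopes alone, 7×3, 9×3, or a single foot term). These test different hypotheses on different degrees of freedom, and a SAP should settle that choice beforehand.

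**Working it through.** **1. The protocol's own figures reproduce.**
- Surfaces: 1 flat + 2 + 2 along the walking direction + 2 cross-slopes = 7. The protocol calls the first group five slopes, so it counts ± as two.
- Slips: 3×5 + 3×2×2 = 15 + 12 = 27.

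**2. The SAP list does not.** By the same convention it has 1 + 2 + 2 + 2 + 2 = 9 levels, against seven stated. Three readings are possible:

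| Reading of the ML entries | Levels | Slips implied |
|---|---|---|
| ± is a slip of the pen | 7 | 27, but only with a foot term on the cross-slopes (7×3 = 21 without it) |
| ± stands for the slipped foot | 9 | 9×3 = 27 |
| ± means two tilt directions, both feet slipped on each | 9 | 15 + 3×2×4 = 39 |

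The third reading contradicts the 27. The first needs a foot term that the SAP lacks. The second contradicts the stated seven.

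**3. What a seven-level slope-only model pools.** It has seven condition cells against 27 designed. Each flat or AP level averages 3 timings. Each cross-slope level averages 3 timings × 2 feet = 6 slips. The feet are merged in 12/27 = 44% of slips and the timings in 27/27.

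**4. Effect on standard errors.** The documents give no sample size, SD or effect size, so this part is illustrative. Assumptions: N = 10, 20 or 40 participants; participant effects in the model; additive effects in residual-SD units; the same foot difference on both cross-slopes; evenly spaced timing effects.

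Let the feet sit at +d and −d (difference 2d) and the timings at +t, 0, −t (early-to-late difference 2t). The omitted sums of squares are:
- foot: 12N·d²
- timing: (9 + 9)N·t² = 18N·t²

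The ratio of the estimated SE to its correct value is √(1 + omitted SS / residual df). Residual df are:
- slope only: 26N − 6 = 254, 514, 1034
- slope + timing: 26N − 8 = 252, 512, 1032
- slope × timing: 26N − 20 = 240, 500, 1020

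Examples at a difference of 2 SD (d = t = 1), N = 10:
- timing omitted: √(1 + 180/254) = 1.307
- foot omitted, timing crossed with slope: √(1 + 120/240) = 1.225
- both omitted: √(1 + 300/254) = 1.477

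Rise in estimated SE over N = 10 to 40:

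| Omitted | 0.5 SD | 1 SD | 2 SD |
|---|---|---|---|
| Foot (timing modelled, additive or crossed) | 1.4-1.6% | 5.7-6.1% | 21.0-22.5% |
| Timing (slope only, no foot effect) | 2.2% | 8.4-8.5% | 30.2-30.7% |
| Both, equal differences (t = d) | 3.6% | 13.6-13.8% | 47.0-47.7% |

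The last row corresponds to the list as printed. Adjusting the foot row for 27 order positions, averaged over 20 random orders, changes it by no more than about 0.1 point. Order position therefore does not stand in for foot.

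**5. Bias.** Every surface has the same timing mix, and each cross-slope has equal numbers from each foot. With complete data, surface contrasts averaged over feet and timings have zero bias.

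**6. Angles.** The protocol gives 5.0 and 10.0 degrees; the SAP gives 5.3 and 10.6. The documents do not show which were used.

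**The case against.** The best counter-argument on foot is that the ML sign already codes it: nine levels times three timings is exactly 27, with two entries per cross-slope matching two feet. On that reading no slips are pooled over feet. This stands as a possibility, so the 44% is conditional. It does not rescue the text, because seven levels is then wrong and the sign is never defined.

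On timing, the SAP says the model will examine diverse slip conditions for all aims, and a plural heading followed by a lone item a) looks like a dropped line rather than a decision to fit slope alone. That is plausible, but the general sentence names neither timing nor foot, and the list is where the SAP specifies its factors.

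The SE percentages are also open to challenge, since they follow directly from the assumed effects and are not evidence about this trial. That is accepted. Their narrow ranges reflect only N and df, and the joint row needs equal timing and foot differences. Even spacing of timings is the mildest case: if mid stance equals early stance, the timing sum of squares is 24N·t², and at 2 SD the rise is √(1 + 240/254) = 1.395 at N = 10 rather than 1.307.

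Finally, averaging over feet is a legitimate target, and no foot hypothesis is stated. True, but the protocol itself separates the cross-slopes by foot and doubles the slips there.

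**Conclusion.** The concern holds. The mismatch between seven stated and nine listed levels is certain under the protocol's own ± convention, and so is the absence of timing and foot from the Aim 2 list. No reading of the SAP leaves it correct as written.

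The main consequence needs no assumption about effect size: followed with seven levels, the model leaves unestimated a timing effect varied in all 27 slips and a foot effect built into 12 of them (none of the 12 are pooled if the ML sign means foot). The secondary consequence is overstated standard errors, by 3.6% to 47.7% with both factors omitted and equal differences of 0.5 to 2 residual SDs, under the assumptions listed. Balanced surface contrasts are not biased. No effect on power can be calculated, because the documents give no sample size, alpha or power.

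The Aim 1 list also has no foot term although both feet are slipped there (3×3×2 = 18), but this finding is confined to Aim 2.

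**What to change.** Revise the Aim 2 sentence of the Statistical Analysis Plan as follows.

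- Code condition either as one nine-level slope-by-foot factor, or as seven surfaces plus slipped foot nested separately within each of the two cross-slopes (2 df). One foot term shared by both cross-slopes (1 df) is not equivalent. If the foot difference were 0.5 SD on the smaller and 1.0 SD on the larger cross-slope, the shared term would return 0.75 on both, wrong by 0.25 each.
- Add slip timing (three levels) and state whether it is crossed with condition, giving 9×3 = 27 cells.
- Make the level count and the ML ± agree with the chosen coding, and define the sign if it is kept.
- Reconcile the angles between Aim 2 Specific Methods and the SAP.

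The cost is wording and a few fixed-effect df. Timing takes the model from 6 to 8 (or 20 if crossed with the seven slopes). Foot takes it from 8 to 10 (or from 20 to 26 if crossed with timing). No new data are needed provided the slipped foot is recorded for each slip.
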